## 16.3 Clinical Laboratory Evaluation

*Analysis sets: Safety-Induction Analysis Set, Safety-Maintenance Analysis Set*

### 16.3.1 Hematology and Chemistry Parameters

Laboratory results will be classified according to the NCI-CTCAE criteria version 4.03. Non-numerical qualifiers (with the exception of fasting flags) will not be taken into consideration in the derivation of CTCAE criteria (e.g., hypokalemia Grade 1 and Grade 2 are only distinguished by a non-numerical qualifier and therefore Grade 2 will not be derived). Additional laboratory results that are not part of NCI-CTCAE will be presented according to the categories: below normal limit, within normal limits and above normal limit (according to the laboratory normal ranges).

The worst grade during the on-treatment period will be summarized per treatment group considering only subjects with post baseline laboratory samples: Laboratory tests by NCI-CTC grade (0, 1, 2, 3, 4).

Quantitative data will be summarized using simple descriptive statistics (mean, SD, median, Q1, Q3, minimum, and maximum) of actual values and changes from baseline for each nominal visit over time (unscheduled measurements would therefore not be included in these summaries as described in Section 10). Changes from baseline at each nominal visit over time will also be presented in boxplots. End of Treatment and Safety Follow-Up visits will be summarized separately. The changes

computed will be the differences from baseline. Qualitative data based on reference ranges will be described according to the categories (i.e. Low, Normal, High).

If both central and local labs are collected for a subject, these summary statistics by visit will be based only on the central lab collected data, while summaries of worst on-treatment abnormalities will be based on both local and central lab data.

Abnormalities classified according to NCI-CTCAE toxicity grading version 4.03 will be described using the worst grade. For those parameters which are graded with two toxicities such as potassium (hypokalemia/hyperkalemia), the toxicities will be summarized separately. Low direction toxicity (e.g., hypokalemia) grades at baseline and post baseline will be set to 0 when the variables are derived for summarizing high direction toxicity (e.g., hyperkalemia), and vice versa.

Subjects without post baseline laboratory samples will be excluded from analyses with respect to values after the baseline.

For **WBC differential counts** (total neutrophil [including bands], lymphocyte, monocyte, eosinophil, and basophil counts), the absolute value will be used when reported. When only percentages are available (this is mainly important for neutrophils and lymphocytes, because the CTCAE grading is based on the absolute counts), the absolute value is derived as follows:

$$\text{Derived differential absolute count} = (\text{WBC count}) \times (\text{Differential \%value} / 100)$$

If the range for the differential absolute count is not available (only range for value in % is available) then Grade 1 will be attributed to as follows:

- Lymphocyte count decreased:
  - derived absolute count does not meet Grade 2-4 criteria, and
  - % value < % LLN value, and
  - derived absolute count  $\geq 800/\text{mm}^3$
- Neutrophil count decreased:
  - derived absolute count does not meet Grade 2-4 criteria, and
  - % value < % LLN value, and
  - derived absolute count  $\geq 1500/\text{mm}^3$

For **calcium**, CTCAE grading is based on Corrected Calcium. Corrected Calcium is calculated from Albumin and Calcium as follows:

$$\text{Corrected Calcium (mg/dL)} = \text{Calcium (mg/dL)} - 0.8 [\text{Albumin (g/dL)} - 4]$$

**Liver function tests:** Alanine aminotransferase (ALT), aspartate aminotransferase (AST), and total bilirubin are used to assess possible drug induced liver toxicity. The ratios of test result over upper limit of normal (ULN) will be calculated and classified for these three parameters during the on-treatment period.

---

Summary of liver function tests will include the following categories. The number and percentage of subjects with each of the following during the on-treatment period will be summarized by treatment group:

- $ALT \geq 3 \times ULN$ ,  $ALT \geq 5 \times ULN$ ,  $ALT \geq 10 \times ULN$ ,  $ALT \geq 20 \times ULN$
- $AST \geq 3 \times ULN$ ,  $AST \geq 5 \times ULN$ ,  $AST \geq 10 \times ULN$ ,  $AST \geq 20 \times ULN$
- $(ALT \text{ or } AST) \geq 3 \times ULN$ ,  $(ALT \text{ or } AST) \geq 5 \times ULN$ ,  $(ALT \text{ or } AST) \geq 10 \times ULN$ ,  $(ALT \text{ or } AST) \geq 20 \times ULN$
- $TBILI \geq 2 \times ULN$
- Concurrent  $ALT \geq 3 \times ULN$  and  $TBILI \geq 2 \times ULN$
- Concurrent  $AST \geq 3 \times ULN$  and  $TBILI \geq 2 \times ULN$
- Concurrent  $(ALT \text{ or } AST) \geq 3 \times ULN$  and  $TBILI \geq 2 \times ULN$
- Concurrent  $(ALT \text{ or } AST) \geq 3 \times ULN$  and  $TBILI \geq 2 \times ULN$  and  $ALP > 2 \times ULN$
- Concurrent  $(ALT \text{ or } AST) \geq 3 \times ULN$  and  $TBILI \geq 2 \times ULN$  and  $ALP \leq 2 \times ULN$  or missing

Concurrent measurements are those occurring on the same date.

Categories will be cumulative, i.e., a subject with an elevation of  $AST \geq 10 \times ULN$  will also appear in the categories  $\geq 5 \times ULN$  and  $\geq 3 \times ULN$ . Liver function elevation and possible Hy's Law cases will be summarized using frequency and percentage.

An evaluation of Drug-Induced Serious Hepatotoxicity (eDISH) plot will also be created, with different symbols for different treatment groups, by graphically displaying

- peak serum  $ALT(/ULN)$  vs peak total bilirubin ( $/ULN$ ) including reference lines at  $ALT = 3 \times ULN$  and total bilirubin  $= 2 \times ULN$ .
- peak serum  $AST(/ULN)$  vs peak total bilirubin ( $/ULN$ ) including reference lines at  $AST = 3 \times ULN$  and total bilirubin  $= 2 \times ULN$ .

In addition, a listing of all TBILI, ALT, AST and ALP values for subjects with a post-baseline  $TBILI \geq 2 \times ULN$ ,  $ALT \geq 3 \times ULN$  or  $AST \geq 3 \times ULN$  will be provided.

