7.1.2 Induction Phase Treatment Period

In this trial, the treatment will be given until PD, significant clinical deterioration (clinical progression), unacceptable toxicity, or any criterion for withdrawal from the trial or trial treatment is fulfilled (see Section 5.5.1).

Treatment during the Induction Phase will consist of:

- 6 cycles of oxaliplatin (85 mg/m² IV on Day 1 every 2 weeks) + leucovorin (200 mg/m² IV on Day 1 every 2 weeks or equivalent levoleucovorin dose) followed by 5-FU (2600 mg/m² IV continuous infusion over 24 hours on Day 1 every 2 weeks,

OR

Oxaliplatin at 85 mg/m² IV on Day 1 with leucovorin 400 mg/m² IV on Day 1 (or equivalent levoleucovorin dose) followed by 5-FU at 400 mg/m² IV push on Day 1 and 2400 mg/m² IV continuous infusion over 46-48 hours (Days 1 and 2) given every 2 weeks (for up to 12 weeks).

OR

- 4 cycles of Oxaliplatin (130 mg/m² IV on Day 1 every 3 weeks) + Capecitabine (1000 mg/m² PO twice daily on Days 1-14). Capecitabine tablets should be swallowed with water within 30 minutes after a meal.

All the laboratory samples and vital signs will be collected prior to each drug administration. Administration of chemotherapy will take place only after relevant results have been checked by a medically qualified person and criteria for dosing have been met.

During the treatment period, the following assessments and procedures will be performed (see [Table 1](#) and [Table 2](#) for the detailed schedule):

- SAEs, AEs and concomitant medications and procedures will be documented at each trial visit.
- ECOG PS will be assessed at Day 1 of each treatment cycle (Screening ECOG PS may be used for Cycle 1 Day 1 if it was performed within 3 days prior to Day 1).
- Physical examinations will be performed on Day 1 of each treatment cycle. Such examinations will include a comprehensive skin examination for tumor.
- Vital signs and body weight will be assessed at each visit.
- Body weight will be assessed at Day 1 of each cycle.
- The laboratory hematology and hemostaseology, will be assessed on Day 1 of each cycle. Core serum chemistry tests will be assessed at Day 1 of each cycle. A full urinalysis will be performed at Screening and the End-of-treatment visit. Subjects should also return to the site as per local institutional practice for any additional routine assessments during chemotherapy.

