7.1.3 Randomization/Re-baseline

At the end of 12 weeks of Induction Phase, subjects enter a 10-day Re-baseline period and the following assessments and procedures will be performed (see [Table 3](#) to [Table 6](#) for detailed schedule):

- Review of eligibility criteria
- The subject-reported outcomes / QoL assessments will be completed by subjects prior to any other trial-related procedures.
- AEs and concomitant medications and procedures
- ECOG PS
- 12-lead ECG
- Physical examination, including a comprehensive skin examination for tumor
- Vital signs and body weight
- Laboratory hematology, hemostaseology, full serum chemistry (including core chemistry) and full urinalysis
- Urine or serum β -hCG pregnancy test for females of childbearing potential
- Free T₄ and TSH

- Cardiac troponin levels will be collected from Re-baseline up to 12 weeks in the Maintenance Phase.

Cardiac troponin levels will be evaluated centrally. Local laboratories may be used at the discretion of the Investigator as clinically needed for safety management/treatment decision of the subject. Measurement of cardiac troponin T (cTnT) is preferred, however cardiac troponin I (cTnI) may be substituted where cTnT is not available at the local laboratory. The same subunit (cTnT or cTnI) measured at the Re-baseline visit should be measured consistently throughout the study in each patient. At the Re-baseline visit, clinically significant positive results should be further assessed as per local SOC to rule-out concurrent cardiac conditions which would make the patient ineligible for the study as per exclusion criteria. During the study, clinically significant new elevations suggestive of myocarditis should be assessed as per [Table 11](#). Additional tests should also be performed when clinically indicated.

Subjects who progress during the Induction Phase or who are determined to have PD during the Re-baseline period will be discontinued from the trial.

Subjects without PD will be randomly assigned to receive maintenance treatment with either avelumab or continuation of the same regimen of chemotherapy from the Induction Phase. Subjects who demonstrate a response during the Induction Phase that renders their measurable disease no longer measurable at the time of the Maintenance Phase can be randomized.

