- Physical examinations will be performed through Week 13 or while the subject is on-treatment. After Week 13, the physical examination will occur every 6 weeks. Such examinations will include a comprehensive skin examination for tumor.
- Vital signs and body weight will be assessed in each treatment visit.
- The laboratory hematology, hemostaseology will be assessed at each visit.
- Serum chemistry tests will be assessed as follows:
 - Full serum chemistry at Re-baseline for all subjects
 - Core serum chemistry:
 - Subjects on the avelumab arm: Week 1, Week 3, Week 5, Week 7, Week 9, Week 11, Week 13, and every 2 weeks thereafter.
 - Subjects on BSC-only with no active therapy: Week 1, Week 4, Week 7, Week 10, Week 13, and every 3 weeks thereafter.
 - Subjects on the chemotherapy doublet arm receiving oxaliplatin + capecitabine on Week 1, Week 4, Week 7, Week 10, Week 13 and every 3 weeks thereafter.
 - Subjects on the chemotherapy doublet arm receiving oxaliplatin + 5-FU on Week 1, Week 3, Week 5, Week 7, Week 9, Week 11, Week 13, and every 2 weeks thereafter.
- A basic urinalysis (dipstick) will be at Week 1, Week 7, Week 13, and every 12 weeks thereafter. If the basic urinalysis is abnormal, a full urinalysis should be performed.
- A urine or serum β -hCG pregnancy test will be performed at the visits indicated in the Assessment Schedules (for females of childbearing potential).

CCI

- Blood samples for PK determinations will be collected from all subjects in the avelumab arm on or before Day 1 (Week 1) prior to the first administration of study drug, within 2 hours prior to each trial drug administration at Weeks 3, 5, 7 (every 2 weeks), at Weeks 13, 19, and 25 (every 6 weeks), and then at 12-week intervals while on-treatment up to Week 109 (2 years from randomization). Post-trial drug administration samples will be collected at the end of infusion (within 15 minutes) at Weeks 1, 7, and 25. Samples will be collected at the End-of-Treatment visit and the 30-day Safety Follow-up visit, except for subjects still on trial treatment beyond Week 109.

CCI

CCI

CCI

- Trial drug infusion at each trial visit (once every 2 or 3 weeks).
- Premedication as described in Section 5.1.2.2.1
- Cardiac troponin levels will be collected from Re-baseline up to 12 weeks in the Maintenance Phase.

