7.1.5 End of Treatment

Subjects must undergo an End-of-Treatment visit after discontinuation of IMP for any reason. This visit should be performed within 7 days of the decision to discontinue treatment but before any new antineoplastic therapy is started (if possible), whichever occurs earlier. See Table 1 through Table 7 for the assessments to be performed.

All AEs will be collected up until the 30-Day Safety Follow-up visit.

At the End-of-Treatment visit, the following assessments will be performed:

- Documentation of AEs and concomitant medication and procedures
- Physical examination, including vital signs, and body weight
- 12-lead ECGs
- Laboratory hematology, hemostaseology, full serum chemistry, pregnancy test, and full urinalysis.
- T₄ and TSH
- ECOG PS

CCI

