7.1.6 Safety Follow-up Visit

All subjects will have a subsequent visit scheduled 30 days (\pm 5 days) after the last administration of trial drug, and will be contacted by phone 90 days (\pm 1 week) after the last administration of trial drug.

The visit will include the following full assessment of safety parameters (see [Table 3](#) to [Table 6](#)):

- The subject-reported outcomes / QoL assessments will be completed by subjects prior to any trial-related procedures
- Documentation of AEs and concomitant medication and procedures
- ECOG PS
- Physical examination including vital signs, body weight, and skin tumor extent
- The laboratory hematology, hemostaseology, full serum chemistry, and basic urinalysis (dipstick plus microscopic evaluation). If the basic urinalysis is abnormal, a full urinalysis should be performed.
- A urine β -hCG pregnancy test (in females of childbearing potential) will be conducted.
- T₄ and TSH levels

CCI

All AEs will be documented until the 30-day Safety Follow-up visit. Subjects with an ongoing SAE at the 30-day Safety Follow-up visit must be monitored and followed up by the Investigator until stabilization or until the outcome is known, unless the subject is documented as “lost to

follow-up". After this visit, all SAEs and all treatment-related non-serious AEs need to be documented until the 90-day Safety Follow-up Phone Call. All subjects will be contacted by phone 90 days after the last administration of trial drug to collect information on new or ongoing SAEs and treatment-related non-serious AEs.

If another antineoplastic therapy is administered before the end of this 30-day period, the 30-day Safety Follow-up visit should be conducted, if possible, prior to the start of this new therapy.

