7.4.3 Clinical Laboratory Assessments

All laboratory samples that are detailed in the Schedule of Assessments (see Table 1 to Table 7) must be collected, and sent to the central laboratory for analysis. Serum β -hCG pregnancy tests may be analyzed locally.

Sample for complete blood count and core chemistry must be available and reviewed prior to dose administration. Results of all central laboratory testing will be transferred to the clinical database.

Urinalysis and urine pregnancy testing will be done locally.

Local laboratory samples may be drawn and if collected are required to be recorded in the eCRFs.

In the case of liver function test (LFT) elevations (AST, ALT and/or total bilirubin) requiring additional lab draws (according to guidelines set forth in Table 11 Management of irAEs), an unscheduled lab draw should be sent to the central laboratory for analysis.

Cardiac troponin levels will be collected from Re-baseline up to 12 weeks in the Maintenance Phase. Cardiac troponin levels will be evaluated centrally. Local laboratories may be used at the discretion of the Investigator as clinically needed for safety management/treatment decision of the subject. Measurement of cTnT is preferred, however cTnI may be substituted where cTnT is not available at the local laboratory. The same subunit (cTnT or cTnI) measured at the Re-baseline visit should be measured consistently throughout the study in each patient. At the Re-baseline visit, clinically significant positive results should be further assessed as per local SOC to rule-out concurrent cardiac conditions which would make the patient ineligible for the study as per exclusion criteria. During the study, clinically significant new elevations suggestive of myocarditis should be assessed as per Table 11. Additional tests should also be performed when clinically indicated.

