The report of the results must be retained as a part of the subject's medical record or source documents. Blood samples for the full safety tests listed in Table 12 will be taken from nonfasted subjects during the Screening Phase (28 days prior to entering the Induction Phase); during the Treatment Phase as specified in Table 1, Table 2, Table 3, Table 4, Table 5, Table 6; at the End-of-Treatment visit; and at the Safety Follow-up visit. The T₄, TSH, and urinalysis will only be assessed at the time points defined in Table 1, Table 2, Table 3, Table 4, Table 5, and Table 6. If confirmation of a subject's postmenopausal status is necessary, an FSH level will also be performed at Screening, see Section 7.1.

Table 12 Clinical Laboratory Assessments

Full Chemistry	Core Chemistry ^a	Hematology
Albumin	Alkaline phosphatase	Absolute lymphocyte count
Alkaline phosphatase	ALT	Absolute neutrophil count
ALT	Amylase	Hematocrit
Amylase	AST	Hemoglobin
AST	BUN/total urea	Platelet count
GGT	Calcium	RBC count
BUN/total urea	Chloride	White blood cell count and differential count
Calcium	Creatine kinase	Reticulocytes
Chloride	Creatinine	MCH
Cholesterol	Glucose	Mean corpuscular volume
Creatine kinase	LDH	MCHC
Creatinine	Lipase	
CRP	Phosphorus/Phosphates	
Glucose	Magnesium	Hemostaseology
LDH	Potassium	aPTT
Lipase	Sodium	Prothrombin time/INR
Phosphorus/Phosphates	Total bilirubin	
Magnesium		Basic Urinalysis (dipstick, including macroscopic appearance, bilirubin, blood, color, glucose, ketones, leukocyte esterase, nitrite, pH, protein, specific gravity, urobilinogen)
Potassium		
Sodium		

Full Chemistry	Core Chemistry ^a	Hematology
Total bilirubin		Full urinalysis (dipstick plus microscopic evaluation) to be performed only at the Screening, Re-baseline, and End of Treatment visits and a basic urinalysis prior to each administration of the trial treatment at Week 1, Week 7, Week 13, every 12 weeks thereafter, and at 30-day Safety Follow-up visit.
Total protein		
Uric acid		Totality of binding CCI
Triglycerides		
		TSH and T ₄
Hormone		
FSH (yes/no if applicable)		

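### SAP 16.3.1 grades calcium only after albumin correction, but scheduled dosing visits measure calcium without albumin, so the calcium grade and shift tables omit those results

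*SAP*

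**What the plan says.** **Grading rule.** SAP 16.3.1 states for calcium: "CTCAE grading is based on Corrected Calcium. Corrected Calcium is calculated from Albumin and Calcium as follows". The formula is corrected calcium = calcium - 0.8 × (albumin - 4), with calcium in mg/dL and albumin in g/dL. Nothing follows on which albumin to use or what to do without one. The same section puts calcium, in both the low and high direction, into the CTCAE grade table and the shift table from baseline to worst on-treatment grade. SAP Table 8 asks for graded laboratory tables in three blocks: Safety-Induction, and Safety-Maintenance for each phase.

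**Panels.** Protocol 7.4.3, Table 12, lists calcium under full chemistry and under "Core Chemistry". Albumin appears under full chemistry only.

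**Schedule.**
- Induction (Protocol 7.1.2): "Core serum chemistry tests will be assessed at Day 1 of each cycle".
- Maintenance (Protocol 7.1.4): core chemistry at each scheduled visit from Week 1, every 2 weeks (avelumab, oxaliplatin + 5-FU) or every 3 weeks (oxaliplatin + capecitabine, BSC-only).
- Full chemistry: Screening; Re-baseline (7.1.4: "Full serum chemistry at Re-baseline for all subjects"); End of Treatment (7.1.5: "Laboratory hematology, hemostaseology, full serum chemistry, pregnancy test, and full urinalysis"); and the Maintenance 30-day visit (7.1.6: "The laboratory hematology, hemostaseology, full serum chemistry, and basic urinalysis").

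**Related rules.** SAP section 10 evaluates data as reported, without imputation unless the SAP specifies it. SAP 16.3.1 uses local as well as central results for worst on-treatment abnormalities, and Protocol 7.4.3 adds: "Local laboratory samples may be drawn and if collected are required to be recorded in the eCRFs".

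**The concern.** The grading rule needs two analytes, and the visits that produce most of the calcium results supply one. A high-grade calcium at a dosing visit would then be missing from a table meant to show the worst grade on treatment. The table would describe mainly the end of treatment.

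The text also leaves programmers a choice. They could grade same-date pairs only, carry an earlier albumin forward, or grade uncorrected calcium. The first follows the SAP literally. The other two depart from it but would fill the gap. The three can give different tables, and the choice recurs in all three blocks of SAP Table 8.

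**Working it through.** There is no plan figure to reproduce, so the check is a comparison of panels and a count of visits.

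**1. Panels (Protocol Table 12).** Full chemistry has 24 analytes and core has 17. The difference is albumin, GGT, cholesterol, CRP, total protein, uric acid and triglycerides. Calcium is in core; albumin is not.

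**2. Scheduled dosing visits with both analytes.** None, in any schedule of Protocol Tables 1 to 6.

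**3. Maintenance samples after Day 1 (Protocol Tables 3 to 6).** Core visits on the 2-weekly schedule are Weeks 3, 5, 7, 9, 11 and 13, so n = 6, or 12 through Week 25. On the 3-weekly schedule they are Weeks 4, 7, 10 and 13, so n = 4, or 8 through Week 25.

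The gradable share is 1/(n + 1) when only End of Treatment carries albumin inside the on-treatment period, and 2/(n + 2) when the 30-day visit also falls inside it.

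| Last dose | Schedule | n | End of Treatment only | Plus in-window 30-day visit |
|---|---|---|---|---|
| Week 13 | 2-weekly | 6 | 1/7 = 14% | 2/8 = 25% |
| Week 13 | 3-weekly | 4 | 1/5 = 20% | 2/6 = 33% |
| Week 25 | 2-weekly | 12 | 1/13 = 8% | 2/14 = 14% |
| Week 25 | 3-weekly | 8 | 1/9 = 11% | 2/10 = 20% |

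The 30-day visit may fall on days 25 to 35 after last dose. The on-treatment period in SAP section 10 ends at last dose + 30 days, or earlier if new anti-cancer drug therapy starts. Days 25 to 30, 6 of the 11 permitted days, are inside. BSC-only subjects follow the 3-weekly visits, but their period runs to end of assessment + 30 days.

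**4. Induction, all cycles given.** After baseline there are core samples at Weeks 4, 7 and 10 (capecitabine) or Weeks 3, 5, 7, 9 and 11 (5-FU), plus one full panel at Re-baseline or End of Treatment. The shares are 1/4 = 25% and 1/6 = 17%. Under SAP section 10, Re-baseline normally falls inside the Induction on-treatment period. It includes "Laboratory hematology, hemostaseology, full serum chemistry (including core chemistry) and full urinalysis" (Protocol 7.1.3).

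**5. Size of the correction.** By the SAP formula the correction is 0.8 × (4 - albumin). For assumed albumin of 3.5, 3.0, 2.5 and 2.0 g/dL, it is +0.4, +0.8, +1.2 and +1.6 mg/dL. The documents give neither the albumin distribution nor the CTCAE cut points, so the number of grades that would change cannot be computed.

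**6. Search for a rule elsewhere.** The same-date definition in SAP 16.3.1 belongs to the concurrent liver-test categories. The same section does give fallbacks for white-cell differentials reported only as percentages and for missing alkaline phosphatase. It gives none for calcium.

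**The case against.** **The default rules already answer the question.** The formula needs both analytes and imputation is barred, so calcium without albumin is not graded. That is the literal reading, and it stands. It does not remove the problem: it is exactly the reading under which dosing-visit calcium leaves the grade tables.

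**A rule may exist elsewhere.** SAP 4.1 mentions a project-level harmonized SAP. It does so for baseline laboratories, and this SAP cites no calcium rule from it. The supportable statement is that this SAP prints no rule, not that none exists.

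**Albumin may be available from other draws.** Local and unscheduled results count towards worst grade, so the shares above are lower bounds.

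Three stronger readings are tempting, and the documents do not support them:

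- *That calcium safety data are lost.* They are not. By-visit calcium summaries, abnormal-value listings and adverse event reporting do not depend on the correction.
- *That most subjects drop out, or that percentages are heavily diluted by subjects with no gradable value.* One gradable sample is enough to place a subject in the table. SAP 16.3.1 also limits the worst-grade summary to subjects with post-baseline samples, which overrides the general default in SAP section 10 of keeping missing values in the denominator. What stays open is whether that limit is read per test or overall. Subjects still on treatment at cut-off have no scheduled full panel after Maintenance baseline, but their number is not given. The question applies equally to the other full-panel-only graded analytes: albumin, GGT, cholesterol and triglycerides.
- *That baseline is undefined.* SAP section 10 largely settles it as the last central value before first dose. For corrected calcium that is normally Screening in Induction and Re-baseline in Maintenance.

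**Conclusion.** The point holds and is minor. As written, SAP 16.3.1 leaves scheduled dosing-visit calcium ungraded. Among scheduled Maintenance samples, the worst-grade and shift tables rest on roughly 14-33% of post-baseline samples with last dose at Week 13, and 8-20% with last dose at Week 25. The corresponding Induction shares are 17-25%.

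These figures assume that scheduled visits are attended, that the End of Treatment sample falls inside the on-treatment period, and that no local or unscheduled albumin is available. They describe coverage of samples, not a bias in any reported rate. The effect is confined to the descriptive calcium grade and shift tables; efficacy results and type I error are untouched.

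**What to change.** Add to SAP 16.3.1:

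1. The main calcium grades use calcium and albumin from the same date. If the project-level SAP has a pairing rule, cite it instead.
2. A separately flagged supplementary worst-grade and shift table grades calcium without same-day albumin on the uncorrected value. Its footnote says that, by the SAP formula, each 1 g/dL of albumin below 4 makes uncorrected calcium 0.8 mg/dL lower than corrected.
3. For all graded analytes, the denominator is the subjects with at least one gradable post-baseline value for that test in that phase, shown by arm.
4. Baseline corrected calcium is the last central pre-dose result with both analytes in that phase, normally Screening for Induction and Re-baseline for Maintenance.

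The cost is four sentences, one supplementary table and minor programming on existing data. There are two downsides. The same-date set consists mostly of subjects who reached End of Treatment. When albumin is below 4 g/dL, uncorrected grades overstate low calcium and understate high calcium, which is why that table stays separate.

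Carrying albumin forward within an age limit is an alternative, but it recovers little. At nominal visit days, Re-baseline albumin (Day -10 to -1) is 15-24 days old at Day 15, 22-31 at Day 22, 29-38 at Day 29 and 43-52 at Day 43. Through Week 13, a 28-day limit therefore reaches 1 of 6 core results (2-weekly) and 0 to 1 of 4 (3-weekly). A 42-day limit reaches 2 of 6 and 1 of 4. The -4/+2 day visit window can move a result across either limit: Week 5 may fall on Day 25 and Week 7 on Day 39.
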